Study Design:	Study design: Aim 1.1: The monitoring of exhaled CO is based on previous report of assessing exhaled CO in septic patients. Exhaled CO will be determined with an infrared CO analyzer with a sensitivity of 0.1 ppm at 4 hours and 24 hours after PH Aim 1.2: Arterial blood gas (ABG) will be collected from patients before liver resection, at 4 hours and 24 hours after PH. The ABG will be obtained through an arterial line usually placed as part of perioperative monitoring of the patient hemodynamic. This model was found accurate in reflecting HO-1 induction in previous study in patient receiving liver transplantation. Aim 1.3: FLR will be calculated through liver volumetric study from a pre-resectional CT scan. The operative note will be checked for operative details regarding the number of resected hepatic segments and pathological examination of the specimen will allow accurate weight of the resected specimen. According to the resected amount of hepatic parenchyma, three groups of patients will be created (<25%, 25-50% and >50% PH) history of smoking and intraoperative blood transfusion will be reported for each patient. Procedures and Methods - Protocol: For collecting exhaled air specimen, each
	patient will be instructed to exhale completely, and then

take a deep breath, hold it for 20 seconds, and breathe out through D shaped flatpak mouth piece attached to CO analyzer

 
Equipment:
 
A Micro+ CO monitor (Bedfont Scientific Ltd, Wales, England) will be used to analyze CO level in a single breath in exhaled air. The device will be used by applying Anti-bacterial filter and one-way valve for increased infection control.
 
The device has adjustable breath-hold countdown timer for patients who are unable to hold their breath. Calibration will be performed every 6 months as per manufacture recommendation. The device is able to detect and analyze CO concentration within a range of: 0-250 ppm with a sensitivity of 0.1 ppm and accuracy of ±2% in < 20 seconds.
 
Direct evaluation of the COHb level will be performed using an arterial blood gas analyzer (ABL 800 Flex, Radiometer, Copenhagen) and will be reported as % of the total Hb as well as calculated amount in mg/mL.
 

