
 
Assessment of postoperative liver function and regeneration:
 
Liver volumetry will be measured using image
 
J software downloaded from
 
http://rsbweb.nih.gov/ij/. The accuracy of this method was reported in a prior study.
 
Volumetric study will be performed based on CT scan studies obtained as standard of care preoperatively before each liver resection and at one and three months after each resection.
 
Collected data will be reported as percentage compared to the preoperative hepatic volume.
 
Specific Aim 2: To analyze the relationship between HO-1 induction and the quality of post-hepatectomy liver regeneration
 

 
2.1 Analyze the relationship between CO production and the quantity and quality of hepatic regeneration assessed by computed scans liver volumetric study at one and three months after PH and liver function tests.
 
2.2 Determine the relation between hepatic related morbidity in patients undergoing partial hepatectomy and their ability to induce HO-1
 

Study design: Aim 2.1: As CO is uniquely produced by HO reaction; its level was previously validated to check HO-1 induction. Checking this level and comparing outcome of the previously created three groups of patients (<25%, 25-50% and >50% PH) according to their ability to induce HO-1 after PH. Liver regeneration will be evaluated by radiological criteria at one and three months after PH as described above as well as laboratory criteria including liver function tests. Aim 2.2: HO-1 induction was found to offer beneficial protective effect in different clinical and surgical occasions. In this setting of PH, surgical complications in the perioperative (30 days) period graded by Clavien-Dindo Classification will be reported and analyzed regarding its relation with the ability to induce HO-1.
Procedures and Methods: Liver function tests routinely checked on daily basis till normalization will be monitored. This includes serum protein, Albumin, liver enzymes (AST and ALT), alkaline phosphatase and bilirubin level. The duration needed to this normalization will be checked as well as the trend of each of these laboratory parameters. Hepatic morbidity will be evaluated using the criteria used by the international study group of liver surgery being normalization of the INR and bilirubin by POD#5 while the severity

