#### Analyses:

All results will be collected in Excel Document. Analyses of groups based on the extent of liver resection and CO production. Results of different subgroups will be analyzed; comparison between groups will be performed by fisher test, paired and unpaired student t test, main Whitney test or ANOVA with repeated measurements when appropriate. Significance is defined as p<0.05.

Potential problems and alternative strategy: It is possible that HO-1 induction varies according to preoperative and intraoperative factors beside the patient own ability to induce HO-1. The most important known other factors are smoking and intraoperative blood transfusion will be reported in the study, however, other factors may exist and influence the result of this study. Preoperative factors may include preoperative use of chemotherapy and the presence of underlying liver cirrhosis. Intraoperative factors may include operative time and surgical technique (open or minimally invasive). In case of significance variance between patient s in the same group (same percentage of PH) Subgroup analysis including different variants (preoperative chemotherapy, perioperative

	blood transfusion and onen vorsus minimally
	blood transfusion and open versus minimally
	invasive technique) will be used to assess the
	effect of these factors.
Study Population:	125 participants enrolled locally; 125
	enrolled worldwide
Inclusion Criteria:	1-Patients plans to have partial liver
	resection for primary liver pathology or
	metastatic disease
	2-Patients able to comprehend and willing to
	sign the written consent form
Exclusion Criteria:	1-Patients with age less than 18 years
	2-Patients identified as part of the vulnerable
	populations as defined in the current
	application, except women with child bearing
	potential with negative pregnancy test
Study Treatment:	For Aim 1, after the patient's procedure, they
	will have to exhale into the device listed for
	collecting exhaled air specimen.
	For Aim 2, the patient's blood samples that
	are routinely collected after a hepatectomy
	will be used for analyzing serum protein,
	Albumin, AST and ALT, alkaline phosphatase,
	and bilirubin level.
	The duration of an individual's participation
	will be about 3 months +/- 2 weeks.
Study Procedures and Assessments:	Aim 1:
	Procedures and Methods
	- Protocol:
	For collecting exhaled air specimen, each
	patient will be instructed to exhale
	completely, and then

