## 2. STUDY OBJECTIVE

The goal of this proposal is to elucidate the role of HO-1 induction in hepatic regeneration after partial hepatectomy (PH). There is a growing body of evidence that HO-1 induction through CO production has an important role in cellular protection and regeneration. To test this concept, we will monitor endogenous CO production in patients who undergo PH and analyze the relationship between CO production and hepatic regeneration. Using this approach, we will test the following two hypotheses: (1) HO-1 induction after PH is proportional to the extent of the surgical resection, and (2) failure to appropriately induce HO-1 is associated with impaired hepatic regeneration.

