## 7. STUDY ASSESSMENTS

This study is a prospective data collection and thus poses no associated health risks.

- 7.1 Measuring CO by exhaled air using a smokerlyzer device pre-liver resection, and at 4and 24-hours post resection
- 7.2 Measuring carboxyhemoglobin (COHb) in arterial blood gas pre-liver resection, and at 4 and 24 hours post resection
- 7.3 CT scan at 1 and 3 months post liver resection

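### Two hypotheses are tested with p<0.05 applied to every comparison and no deciding CO measure, time or outcome named, so the chance of a false claim of support is well above 5%

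*Combined protocol and SAP*

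**What the plan says.** Section 2 (Study Objective) states that "we will test the following two hypotheses": first, that induction after hepatectomy is proportional to the extent of resection (H1); second, that failure to induce HO-1 is associated with impaired regeneration (H2).

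The Analyses text of the Protocol Summary lists a menu of tests and one threshold: "Significance is defined as p<0.05". The Statistical Analyses row repeats both, once for Aim 1 and once for Aim 2. The same text adds "Results of different subgroups will be analyzed".

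The quantities available for testing are these:

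- **CO.** Section 7 lists "Measuring CO by exhaled air using a smokerlyzer device pre-liver resection", with repeats at 4 and 24 hours, and "Measuring carboxyhemoglobin (COHb) in arterial blood gas pre-liver resection, and at 4 and 24 hours post resection". According to the Protocol Summary, COHb "will be reported as % of the total Hb as well as calculated amount in mg/mL".
- **Laboratory values.** "This includes serum protein, Albumin, liver enzymes (AST and ALT), alkaline phosphatase and bilirubin level". For these, "The duration needed to this normalization will be checked as well as the trend of each of these laboratory parameters".
- **Other outcomes.** CT liver volume at one and three months, post-hepatectomy liver failure, and 30-day complications by Clavien-Dindo grade.

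The Study Endpoints row lists endpoints without ranking them. No primary endpoint, primary CO measure, primary time, testing order, multiplicity rule or exploratory label appears anywhere.

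**The concern.** Each hypothesis is worded as a single claim, but the plan offers many ways to test it and does not say which one counts. CO can be read from breath or blood, at 4 or 24 hours. Regeneration can be read from either CT scan or from laboratory values, and Aim 2 adds morbidity. With one threshold for all of these, an analyst who follows the plan faithfully could report a hypothesis as supported on whichever comparison fell below 0.05. A reader of the report could not tell that from a result for which the study was set up. At stake is whether a positive statement about H1 or H2 carries the 5% error rate that the threshold suggests.

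**Working it through.** The plan states no number of tests and no family-wise error rate, so there is no figure of its own to reproduce. The counts below are a reconstruction, and the correlations are assumptions.

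**Counting Aim 2**

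- CO variables after surgery: 2 measures × 2 times = 4.
- Outcomes, upper count: 6 laboratory values × 2 summaries (time to normalization, trend) + 2 CT volumes + liver failure + Clavien-Dindo = 12 + 2 + 1 + 1 = 16.
- Outcomes, lower count: one summary per laboratory value = 6 + 2 + 1 + 1 = 10.
- Tests: 4 × 16 = 64, or 4 × 10 = 40. If repeated-measures ANOVA merges the two times: 2 × 16 = 32.
- CT volume only, the narrowest reading of H2: 4 × 2 = 8.

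The second COHb unit, contrasts among the three resection groups, and subgroups are not counted.

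**Formulas (k tests, no true effect)**

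- Expected number with p<0.05: 0.05 × k, whatever the correlation.
- Chance of at least one, independent tests: 1 − 0.95^k. For example, 1 − 0.95^64 = 0.962 and 1 − 0.95^8 = 0.337.
- Chance of at least one, two-sided normal tests with common correlation ρ: 1 − ∫ φ(u) [Φ((1.96 − √ρ·u)/√(1−ρ)) − Φ((−1.96 − √ρ·u)/√(1−ρ))]^k du, by numerical integration.

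| Tests k | Expected p<0.05 | ρ = 0 | ρ = 0.5 | ρ = 0.7 | ρ = 0.9 |
|---|---|---|---|---|---|
| 8 (CT only) | 0.4 | 34% | 25% | 19% | 12% |
| 32 (times merged) | 1.6 | 81% | 52% | 35% | 17% |
| 40 (one summary per laboratory value) | 2.0 | 87% | 57% | 38% | 18% |
| 64 | 3.2 | 96% | 68% | 44% | 20% |

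**A second correlation model.** A simulation of the 64 tests as Pearson correlations in 125 patients (6,000 replicates per setting) gave the 4 CO variables one common correlation and the 16 outcomes another. The chance of at least one p<0.05 was 78% with both at 0.5, 56% with both at 0.7, and 26% with both at 0.9. The mean number of false positives stayed near 3.2 throughout.

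**Aim 1.** The number of tests for H1 depends on how the menu is used. Repeated-measures ANOVA, one model per CO measure with one deciding test each, gives 2 tests: 1 − 0.95^2 = 9.75% if independent. All pairwise contrasts of the three groups would give 2 × 2 × 3 = 12 tests: 46% if independent, 32% at 0.5, 13% at 0.9. The plan does not specify pairwise contrasts.

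**The case against.** A reader might infer from the 64-test count that a chance finding is close to certain. The documents do not support that. The 96% needs 64 independent tests with every null true, and independence is the least plausible case: breath CO and COHb reflect one signal in the same patients, and the laboratory values come from the same livers. The count is not the plan's either. The plan lists repeated-measures ANOVA, and says only that laboratory durations and trends will be looked at, not that each is tested against each CO variable.

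A reader might also call p<0.05 a wrong error rate. It is a valid per-comparison threshold, and the plan claims no family-wise rate. What is missing is the designation of a deciding test. Nor do the documents use the word confirmatory; they describe prospective data collection that leaves treatment alone. But they do not call the study exploratory, and Section 2 says that hypotheses will be tested.

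Three further objections have force:

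- **Direction.** Both hypotheses are directional, so a significant result the wrong way supports neither. If tests are two-sided (sidedness is not stated), the expected number of supporting false positives among 64 is 64 × 0.025 = 1.6, and the chance of at least one is 1 − 0.975^64 = 80% if independent and 35% at correlation 0.5. The benchmark for a single test then falls to 2.5% as well, so the inflation remains.
- **Morbidity.** Liver failure and Clavien-Dindo grade belong to Aim 2.2, not to regeneration as H2 words it. The 8-test row allows for this.
- **Subgroups.** The analyses by chemotherapy, transfusion and technique are conditional on variation within a resection group and are meant to explore those factors, not to decide H1 or H2. They are rightly left out of the count.

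These points reduce the size of the problem. None of them supplies a deciding test.

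**Conclusion.** The point stands as a defect of designation. The plan tests two hypotheses under one unadjusted threshold and does not say which comparison decides either. Assuming 32 to 64 tests for Aim 2 and no true effect, 1.6 to 3.2 results below 0.05 are expected. The chance of at least one runs from 81 to 96% under independence, through 52 to 68% at correlation 0.5, to about 17 to 20% at 0.9. On the narrowest reading of H2, 8 CT tests, the range is 12 to 34%. For H1 it may be as low as about 10% (two independent tests) if the ANOVA route is taken.

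The documents give neither the count nor the correlations, so no single figure can be defended. The conclusion needs only that the rate exceeds 5%, and it does in every case examined.

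**What to change.** Before analysis, name one deciding test per hypothesis:

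- **H1:** one CO measure at one post-operative time against the extent of resection, with extent defined in one way.
- **H2:** the same CO measure against CT regeneration at one of the two planned scans.

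The sponsor chooses the measure and the times. COHb at 24 hours is one example; the documents give no reason to prefer it over the alternatives. What matters is that the choice is written down before results are analysed.

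Test the two with Holm at an overall 0.05: the smaller p-value is compared with 0.025 and, if it passes, the other with 0.05. Label all other comparisons and all subgroups exploratory, and state that they will not be cited as support for either hypothesis.

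The cost is wording and minor analysis work, with no new patients, samples or scans. Some secondary results can no longer be called significant, and Holm slightly lowers power for the two deciding tests. That loss cannot be quantified here, because the plan gives 125 participants without an effect size, a standard deviation or a power calculation.

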## 5.1 Inclusion Criteria

-Patient plans to have partial liver resection for primary liver pathology or metastatic disease

-Patients is able to comprehend and willing to sign the written consent form

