## 5.2 Exclusion Criteria

-Patients with age less than 18 years

-Patients identified as part of the vulnerable populations as defined in the current application, except women with child bearing potential with negative pregnancy test

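### The plan names cirrhosis as a factor that may alter HO-1 induction and the result, but does not commit to recording it or to adjusting the Aim 2 comparisons for it

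*Combined protocol and SAP*

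**What the plan says.** **Who enters.** Section 5.1 admits: "Patient plans to have partial liver resection for primary liver pathology or metastatic disease". Section 5.2 excludes minors and vulnerable populations and says nothing about cirrhosis.

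**What is named as a threat.** The Protocol Summary, under potential problems and alternative strategy, says that HO-1 induction may vary for reasons other than the patient's own capacity. It lists: "Preoperative factors may include preoperative use of chemotherapy and the presence of underlying liver cirrhosis". Operative time and surgical approach are named as intraoperative factors.

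**What is to be recorded.** Aim 1.3 in the Protocol Summary commits to this: "history of smoking and intraoperative blood transfusion will be reported for each patient". The analysis text repeats it: "smoking and intraoperative blood transfusion will be reported in the study, however, other factors may exist and influence the result of this study". Cirrhosis is in neither place.

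**What is to be analysed.** The trigger is "In case of significance variance between patient s in the same group (same percentage of PH", with no threshold. The response begins "Subgroup analysis including different variants (preoperative chemotherapy, perioperative" and the bracket continues with transfusion and open versus minimally invasive surgery. Cirrhosis is not in it.

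**Which tests are used.** For both aims the summary lists Fisher, paired and unpaired t, Mann-Whitney and repeated-measures ANOVA at p<0.05. No stratified or covariate-adjusted analysis is specified. Patients are grouped by percent resected (<25%, 25–50%, >50%) and by CO production.

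**The concern.** The second hypothesis in Section 2 is that "failure to appropriately induce HO-1 is associated with impaired hepatic regeneration". It is tested in an observational cohort, so nothing balances liver quality between patients with a high and a low CO response. The plan supplies one arm of a confounding path itself: cirrhosis may change HO-1 induction. The other arm, from cirrhosis to regrowth, liver tests or liver failure, is clinically plausible but not stated.

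If both arms act in the same direction, low CO and poor recovery travel together without any HO-1 effect. If they act in opposite directions, a true relation is weakened or hidden. Grouping by percent resected does not remove this, because a cirrhotic and a non-cirrhotic patient with the same percent resected fall in the same group. At stake is whether an Aim 2 finding can be read as concerning HO-1 rather than the underlying liver.

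**Working it through.** **1. Text check.** Factors named in the Protocol Summary, against the two places where the plan acts on them:

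| Factor | Reported per patient | In subgroup bracket |
|---|---|---|
| Smoking | yes | no |
| Transfusion | yes | yes |
| Preoperative chemotherapy | no | yes |
| Open vs minimally invasive | no | yes |
| Operative time | no | no |
| Cirrhosis | no | no |

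Chemotherapy and cirrhosis are named in the same sentence, and only chemotherapy reaches the subgroup bracket.

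**2. Inputs for size.** From the Protocol Summary: N = 125 and alpha 0.05 (sidedness not stated; two-sided taken here). The documents give no power, SD, effect size or cirrhosis prevalence, so there is no figure of the plan's to reproduce. Assumed: a cirrhotic share p of 15–35%; shifts d₁ in CO response and d₂ in outcome of 0.5–1 SD in the same direction; no relation between CO and outcome within liver type.

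**3. Spurious correlation.** With v = p(1−p),

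r = v·d₁·d₂ / √[(1 + v·d₁²)(1 + v·d₂²)].

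- p = 0.15, both shifts 0.5: v = 0.1275; r = 0.0319/1.0319 = 0.03.
- p = 0.25, shifts 0.5 and 1: v = 0.1875; r = 0.09375/√(1.0469 × 1.1875) = 0.08.
- p = 0.25, both shifts 1: r = 0.1875/1.1875 = 0.16.
- p = 0.35, both shifts 1: v = 0.2275; r = 0.2275/1.2275 = 0.19.

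For scale, the correlation detectable with 80% power at N = 125 is tanh[(1.960 + 0.842)/√122] = 0.25. The spurious values are all below it.

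**4. False-positive rate at nominal 5%, by simulation.**

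| Analysis | Range over the assumed grid |
|---|---|
| Whole-cohort correlation, n = 125 | about 6–55% |
| High/low-CO (median-split) t test, n = 125 | about 5–40% |
| Same t test in one resection group, n = 125/3 ≈ 42 | about 5–17% |

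At 25% cirrhotic, the correlation test rejects in 16% of trials with shifts of 0.5 and 1 SD, and in 42% with 1 SD on both. The median-split t test gives 29% in the latter case. The third row assumes equal resection groups, which the plan does not promise.

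**5. After adjustment.** With cirrhosis recorded and adjusted for, over a wider grid (10–40% cirrhotic, both shifts 0.5–1 SD, 4,000 runs per setting), the correlation test rejects in 4.4–5.4%. The simulation standard error at 5% is √(0.05 × 0.95/4000) = 0.34 percentage points, so this is consistent with the nominal level.

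**The case against.** The strongest reply is that the plan may already cover cirrhosis. The subgroup sentence introduces its bracket with an inclusive word and closes by referring back to the factors just discussed, of which cirrhosis is one. Operative time is also named and missing from the bracket, so the bracket may be an abbreviated restatement. This stands against one tempting reading, that the plan deliberately excludes cirrhosis from its subgroup analysis. The text is ambiguous on that. It does not answer the point, because a conditional subgroup analysis with no trigger threshold does not adjust the Aim 2 comparison, whatever the list contains.

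Other replies:

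- **Baseline.** CO is measured before resection, and volume is expressed relative to preoperative volume. If CO is analysed as change, a stable effect of cirrhosis on CO level cancels. An effect on induction itself does not, and that is the effect the plan warns of. The assumed shifts should be read as shifts in CO response.
- **Data.** Section 3 collects specimen pathology, laboratory and radiology results, and Section 4 uses medical records for eligibility. Cirrhosis status may therefore be retrievable, and a reader should not infer that it is lost. No section commits to extracting it.
- **Eligibility.** The inclusion criterion does not mention cirrhosis. Its presence follows from the absence of an exclusion and from the plan's own warning; the share is unknown and could be small.
- **Resection practice.** A reader might add that cirrhotic patients will be concentrated in the smaller-resection groups. Nothing in the documents supports this, and the point does not need it.

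**Conclusion.** The concern holds in a limited form. The plan identifies a potential confounder of its second hypothesis and then commits neither to recording it nor to handling it in the main Aim 2 comparisons. That much rests on the text alone.

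The size rests on assumptions about prevalence, direction and strength, and on the inference that cirrhosis affects the outcomes. Within the assumed range the inflation runs from negligible to serious, depending on the test. A reader might take the upper figures of 42–55% as the error rate of this plan. The documents do not support that: those figures belong to a whole-cohort correlation, which is not among the listed tests. A test closer to the list gives up to about 40% in the full cohort and about 17% within one resection group, both at the strongest assumed shifts. Nor do the documents give a direction; masking of a real effect is as open as mimicry. This is a change the sponsor should make, not a fatal flaw.

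**What to change.** 1. Record cirrhosis (yes/no) and indication (primary or metastatic) for every patient, from the pathology report and medical record already in use.
2. Add cirrhosis explicitly to the factor list in the Protocol Summary.
3. Prespecify that the main Aim 2 comparisons of CO change from baseline with regeneration and liver tests are adjusted for or stratified by cirrhosis. Linear regression or ANCOVA with resection extent and cirrhosis would serve, or a stratified rank test.
4. For morbidity, use a stratified exact or Mantel-Haenszel analysis where the number of events allows.
5. Report the Aim 2 result in non-cirrhotic patients as a sensitivity analysis.

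The cost is one or two data fields and a small loss of precision. It is more than one added term, because Fisher and Mann-Whitney tests take no covariate: a simple adjusted or stratified analysis has to replace the listed two-group tests for these comparisons. Patient care is unchanged.

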## **Protocol Summary**

Protocol Number:	HP-00054854
Protocol Title:	Postoperative Heme Oxygenase Induction and Carbon Monoxide Production as a Novel Method to Assess Hepatic Regeneration and Predict Hepatic Related Morbidity After Partial Hepatectomy
Study Rationale:	The goal of this proposal is to elucidate the role of HO-1 induction in hepatic regeneration after partial hepatectomy (PH). There is a growing body of evidence that HO- 1 induction through CO production has an important role in cellular protection and regeneration. To test this concept, we will monitor endogenous CO production in patients who undergo PH and analyze the relationship between CO production and hepatic regeneration. Using this approach we will test the following two hypotheses: (1) HO-1 induction after PH is proportional to 
Study Objectives:	Specific Aim 1: To monitor the extent of HO-1 induction (by measuring endogenous CO production) in relationship to the extent of hepatic resection 1.1 Monitor CO in exhaled air of patients before liver resection, at 4 hours and 24 hours after PH 1.2 Monitor carboxyhemoglobin(COHb) in the arterial blood gas of patients before liver resection at 4 hours and 24 hours after PH 1.3 Analyze the relationship between CO production and the extent of hepatic resection assessed by computed scans liver volumetric study at one and three months after PH, size and weight of the resected specimen and operative report. Specific Aim 2: To analyze the relationship between HO-1 induction and the quality of post-hepatectomy liver regeneration after PH

	
 
2.1 Analyze the relationship between CO production and the quantity and quality of hepatic regeneration assessed by computed scans liver volumetric study at one and three months after PH and liver function tests after PH.
 
2.2 Determine the relation between postoperative liver related morbidity in patients undergoing PH and the extent of postoperative HO-1 induction
 

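### A proportionality hypothesis is tested on three extent groups with no fixed role for pre-resection CO or smoking; prespecify a regression on continuous extent adjusted for both

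*Combined protocol and SAP*

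**What the plan says.** All references are to the combined protocol and SAP.

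- **Hypothesis.** Section 2 states that HO-1 induction is proportional to the extent of resection.
- **Exposure.** Protocol Summary, Study Design, Aim 1.3 cuts the resected amount into <25%, 25-50% and >50%. It mentions CT volumetry, number of segments and specimen weight, without saying which gives the percentage.
- **Tests.** Analyses lists Fisher's test and "paired and unpaired student t test, main Whitney test or ANOVA with repeated measurements when appropriate". No regression appears, and no test is tied to an endpoint.
- **Baseline.** Study Objectives plans to "Monitor CO in exhaled air of patients before liver resection, at 4 hours and 24 hours after PH", and to measure COHb at the same times. Sections 6 and 7 agree. Study Endpoints names only 4 h and 24 h.
- **Other factors.** "The most important known other factors are smoking and intraoperative blood transfusion will be reported in the study". Two further statements follow: "Preoperative factors may include preoperative use of chemotherapy and the presence of underlying liver cirrhosis", and "Intraoperative factors may include operative time and surgical technique".
- **What is done with them.** One sentence is unconditional but names no subgroup: "Results of different subgroups will be analyzed". The other is conditional: "In case of significance variance between patient s in the same group (same percentage of PH) Subgroup analysis including different variants". Its list covers chemotherapy, perioperative transfusion, and open versus minimally invasive surgery. Smoking, cirrhosis and operative time are not in it.

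**The concern.** A proportional relation is a slope, and the plan never estimates one. Cutting a measured percentage into three groups discards information. Leaving the pre-resection value unassigned means that stable differences between patients, including those due to smoking, may stay in the error term.

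The conditional rule does not fill the gap. It has no statistic, threshold or outcome. Because it looks at spread within one extent group, it cannot show that transfusion differs between groups. The plan also does not say whether it wants the total association of extent with CO or the association apart from transfusion, and these are different questions.

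At stake are the chance of detecting hypothesis 1 with 125 patients, and how a positive result may be read.

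**Working it through.** The plan gives no effect size, SD or power for its 125 patients, so there is no figure to reproduce. It also gives no smoking prevalence, transfusion rate or pre/post correlation. Everything below except n = 125 and the 0.05 level (taken as two-sided) is assumed.

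**Inputs.** Extent x is uniform on 5-75%, so its SD is 70/√12 = 20.21. Slope b = 0.01 SD of CO per point (0.1 SD per 10 points). CO has SD 1 within smoking stratum. Smoking prevalence is p = 0.2, so v = p(1-p) = 0.16. The smoking shift is d = 2 SD before surgery and kd after it. The pre/post correlation is r.

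**Residual variances**
- Postoperative CO alone: V = 1 + v(kd)²
- Change from baseline: V = 2 - 2r + v·d²(1-k)²
- Baseline as covariate: V = 1 + v(kd)² - (r + v·k·d²)²/(1 + v·d²)
- Baseline and smoking: V = 1 - r²

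For k = 1 and r = 0.5 these are 1.64, 1.00, 1.64 - 1.14²/1.64 = 0.848, and 0.75.

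**Non-centrality**
- Regression (t): 0.01 × 20.21 × √125/√V = 2.259/√V.
- Three groups (F, 2 and 122 df): the group means of x are 15, 37.5 and 62.5, with weights 20/70, 25/70 and 25/70. The between-group variance is 361.6 out of 408.3, or 89%. The parameter is 125 × 0.01² × 361.6/(V + 0.0047) = 4.52/(V + 0.0047).

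For r = 0.5 the adjusted regression has 2.259/√0.75 = 2.61, giving 73.5% power. ANOVA on postoperative CO has 4.52/1.645 = 2.75, giving 29.1%.

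**Power, %: simulated (closed form)**

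| Scenario | 3-group ANOVA, postop | 3-group test, change | Regression, extent only | + baseline | + baseline + smoking |
|---|---|---|---|---|---|
| Shift persists, r = 0.3 | 28 (29.1) | 33 (33.5) | 41 (41.7) | 56 (57.0) | 64 (65.2) |
| Shift persists, r = 0.5 | 28 (29.1) | 46 (45.1) | 41 (41.7) | 69 (68.3) | 73 (73.5) |
| Shift persists, r = 0.7 | 29 (29.1) | 67 (67.5) | 41 (41.7) | 86 (85.9) | 88 (88.1) |
| No smoking effect, r = 0.3 | 44 (45.1) | 33 (33.5) | 61 (61.1) | 65 (65.2) | 64 (65.2) |
| Shift gone after surgery, r = 0.5 | 44 (45.1) | 29 (29.1) | 59 (61.1) | 67 (68.3) | 72 (73.5) |

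The change column is the group-by-time test of a repeated-measures ANOVA with one pre and one post value. With a zero slope (shift persisting, r = 0.5) all five tests reject in 4-5% of trials.

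**Cost of the covariates.** The detectable partial correlation at 80% power is tanh(2.802/√(125-3-k)), with k here the number of covariates. It is 0.248 for k = 0, 0.250 for k = 2 and 0.251 for k = 3.

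**Multiplicity.** Two measures at two times give four tests. If they were independent, the chance of at least one false positive would be 1 - 0.95⁴ = 18.5%, hence one named primary.

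**The case against.** **The listed methods can already use the baseline.** This is fair. A reader might infer that pre-resection CO is ignored, but paired tests and repeated-measures ANOVA are on the menu. With r = 0.7 and a persisting shift, the three-group test on change reaches 67%, so comparing only with postoperative ANOVA would overstate the gain. What stands is that nothing says these methods will be applied to CO from before resection, and that a change score does worse than postoperative CO when r is low or the smoking shift fades.

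**Smoking adds little beyond baseline.** This is also largely right: 56/69/86% without it, 64/73/88% with it. A reader might infer that smoking biases the extent comparison. No section says that smoking varies with extent; if it is balanced, only precision is lost. Adjustment is worth having because it is nearly free.

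**Transfusion is the real confounder, and the proposed primary model leaves it in.** If assumed transfusion rates are 10/25/45% across the groups and transfusion raises CO by 0.5-1.0 SD, an unadjusted comparison of >50% with <25% rejects in 12-29% of trials with no other extent effect. The proposed primary model rejects in 13-32%. These figures therefore support stating the target, not that model. The documents do not say that transfusion rises with extent. Because it occurs during surgery, it may lie on the path from extent to CO.

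**The subgroup rule gives some control.** Once triggered, stratifying by transfusion would be a crude adjustment. The shift from intraoperative to perioperative transfusion is loose wording more than a contradiction.

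**The gain assumes a straight line.** Part of it does. A threshold or plateau would narrow the gap.

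**Conclusion.** The concern holds as a matter of efficiency and prespecification. The planned comparison does not match a proportionality hypothesis, the planned baseline has no fixed use, smoking has no analytic role, and transfusion depends on an undefined trigger.

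Under the main assumptions, power rises from 28-29% (ANOVA on postoperative CO) or 33-67% (three-group test on change) to 64-88%. The source of the gain varies. With no smoking effect and r = 0.3, moving from three groups to continuous extent accounts for 17 of about 20 points (44% to 61%), and adjustment adds little. All sizes rest on assumed inputs and a linear effect.

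The documents do not support a claim that the result will be biased by smoking, or that the recommended primary model removes a transfusion effect. This should be fixed before any outcome is analysed.

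**What to change.** 1. Prespecify as primary a linear regression of postoperative CO on continuous percentage resected, adjusted for the pre-resection value of the same measure and for smoking (current, former, never).
2. Before any outcome is analysed, name one CO measure (exhaled CO or COHb), one time point (4 h or 24 h) and one source for the percentage (CT volumetry, specimen weight or segment count). The other measure-by-time combinations are secondary.
3. Check residuals. If CO is skewed, use a log transformation or a rank-based sensitivity analysis. Show the three group means as a check on linearity.
4. State that the primary model estimates the total association and does not remove any effect through transfusion.
5. Replace the conditional trigger with a prespecified secondary model that adds transfusion in one stated window. Note that it isolates the association apart from transfusion only if no unmodelled factor drives both transfusion and CO.
6. Put cirrhosis and operative time in a sensitivity model where recorded. Keep the chemotherapy and technique subgroups exploratory.
7. Reconcile the sampling text so that pre-resection exhaled CO and COHb are planned consistently. Study Design, Aim 1.1 lists exhaled CO at 4 h and 24 h only, the Summary's Study Treatment entry has patients exhale after the procedure, and sections 3 and 4 describe blood gases from postoperative care. Study Objectives and sections 6 and 7 include a pre-resection measurement.

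**Cost.** The primary model uses 3-4 degrees of freedom out of 125 patients. It also needs coded smoking status and a stated rule for missing pre-resection values. Cirrhosis and operative time must be recorded if the sensitivity model is to be run. Where pre-resection samples are not being taken in practice, the change goes beyond wording.
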